9.4. Data Source

Flatiron Health Database (<https://flatiron.com/real-world-evidence/>).

This retrospective observational study utilized Flatiron Health's longitudinal, demographically and geographically diverse database derived from electronic health record (EHR) data from over 265 cancer clinics (~800 sites of care) including more than 2 million active US cancer patients available for analysis. Across the clinics in the Flatiron Health Network, data become available in near real time after each clinical encounter and contribute to Flatiron's continuously aggregating centralized data set. The patient-level data in the EHRs includes structured data (ie, data points that are organized in a predefined manner, such as dropdown fields that reside in an EHR to capture a patient's gender or date of birth or laboratory data), unstructured data collected via expert human chart abstraction of physician's notes and other free text fields couple with quality controlled natural language processing and business rules technology, and other unstructured documents (ie, information from a portable document format [PDF] laboratory reports or narratives from synoptic reports). Flatiron integrates the structured EHR data with quality controlled curated data from unstructured EHR data into a single data model, where all data are certified HIPAA-compliant with all de-identified patients being assigned a longitudinally stable identifier. Details of de-identification procedure and data management are outline in the Flatiron's parent database protocol (NEIRB#15 159, "The Flatiron Health Analytic Database"). **CCI**

CCI The data used in this analysis already exist within this model, stored in an electronic database.

All data, code to create the MBC dataset, and other technical artifacts are version-controlled and managed within a Flatiron repository. These artifacts are stored and backed up on Flatiron's servers for at least 7 years. All data within the dataset can be traced back to the original source data or documents within the EHR, and appropriate change management and provenance best practices are maintained by Flatiron in the event of a regulatory audit.

Institutional Review Board approval of the study protocol was obtained prior to study conduct, and included a waiver of informed consent. Data provided to third parties were de-identified and provisions were in place to prevent re-identification in order to protect patients' confidentiality.

The data cut-off for this study is November 30, 2018 (or latest Flatiron data cut-off date).

9.5. Study Size

Based on an initial feasibility assessment using Flatiron Health Analytic Database between February 2015 – November 2018, there are 1,367 HR+/HER2- MBC patients who received Palbociclib + AI (including 1,221 Palbociclib + Letrozole, 70 Palbociclib + Anastrozole, and 76 Palbociclib + Exemestane) **and 627 patients who received Letrozole monotherapy** in the database. All eligible patients will be included for descriptive analyses.

9.6. Data Management

Flatiron Health Database (<https://flatiron.com/real-world-evidence/>) collects data through a HIPAA-compliant process that results in de-identified patient data as described above. De-identified data are prepared by Flatiron and transferred securely to Pfizer in a standard flat file format. Once on Pfizer servers, Pfizer staff perform quality assurance on the data, checking that the metadata align with the data dictionary from Flatiron Health, that the number of records equals that expected from the vendor and that the data types and controlled vocabularies are correct in a semi-automated process. The data are then loaded into a secure Pfizer server. Pfizer servers are backed up nightly, and have failover and off-site redundancy. Access to data is limited only to Pfizer colleagues and is monitored with all end user activity is logged. Pfizer maintains copies of all EHR or other real world data in accordance with the FDA's July 2018 Industry Guidance on Use of Electronic Health Record Data in Clinical Investigations (<https://www.fda.gov/downloads/Drugs/GuidanceComplianceRegulatoryInformation/Guidances/UCM501068.pdf>), though Pfizer maintains its data in excess of the guidance – for a minimum of 7 years.

9.6.1. Case Report Forms (CRFs)/Data Collection Tools (DCTs)/Electronic Data Record

As described above, Flatiron Health Database collects data through a HIPAA-compliant process that results in de-identified patient data.

9.6.2. Record Retention

To enable evaluations and/or inspections/audits from regulatory authorities or Pfizer, Flatiron Health has agreed to keep all study-related records, including electronic health records, data curated by Flatiron from unstructured fields within those records, rationale for a curated data point, query code and the dataset provided under this protocol from their larger MBC registry. The records should be retained by Flatiron according to local regulations or as specified in the statement of work, whichever is longer. Flatiron must ensure that the records continue to be stored securely for so long as they are retained.

If Flatiron becomes unable for any reason to continue to retain study records for the required period, Pfizer should be prospectively notified. The study records must be transferred to a designee acceptable to Pfizer.

Study records must be kept for a minimum of 7 years after completion or discontinuation of the study, as expressly agreed to within the statement of work by Flatiron and Pfizer. Pfizer will retain all analysis datasets, code and other artefacts generated over the course of

executing this protocol for at least 15 years or longer if required by applicable local regulations.

Flatiron must obtain Pfizer's written permission before disposing of any records, even if retention requirements have been met.

9.7. Data Analysis

The primary and secondary objectives of the study are to describe patient characteristics, real-world treatment patterns and effectiveness of Palbociclib + AI as initial endocrine based therapy for metastatic breast cancer.

Descriptive analyses: For categorical variables (eg, region, race, and stage at initial diagnosis), data will include the frequency (number of cases) and percentage (%) of total patients observed in each category; for continuous variables (eg, age and time from initial breast cancer diagnosis to metastatic diagnosis), variables will be presented as the mean, standard deviation (SD), median, 25th and 75th percentiles and ranges (minimum and maximum) in some cases. The calculation of percentages will always include the missing category in the case of missing values. Continuous variables may be categorized into intervals, with the distribution of patients (N, %) provided.

Kaplan-Meier curves and landmark analyses will be performed to estimate real-world progression-free survival, overall survival, and time on treatment, time to next line of anti-cancer therapy, and time to first use of chemotherapy. Specifically, landmark time points are 3, 6, 12, 18, 24, 30, and 36 months for rwPFS and rwTR, 0.5, 1, 1.5, 2, 2.5, and 3 years for overall survival, and 3, 6, 12, 18, 24, 30, and 36 months for Time on Treatment with Palbociclib + AI and time to next ant-cancer therapy and to first use of chemotherapy. Ninety-five percent (95%) confidence intervals on the median rwPFS, overall survival, and treatment time will be reported.

The maximum real-world tumor response will be computed for each patient with at least one on-Palbociclib + AI treatment tumor assessment. If a patient has a maximum tumor response of a CR or PR, then the patient will be considered to be a responder. Response rate will be computed using the number of patients with a CR or PR as the numerator and the number of patients with at least 1 on-treatment tumor assessment as the denominator.

[figure not shown]
Subgroup analyses will be conducted according to age, ECOG performance (0, 1, ≥ 2), de novo metastatic, visceral, non-visceral, bone only, disease sites (1, 2, ≥ 3), menopausal status, prior endocrine therapy, prior chemotherapy, prior surgery, prior radiation therapy as appropriate based on availabilities of the data and sample sizes.

The following sensitivity analyses will be performed as appropriate:

1. A subset of patients receiving Palbociclib+AI in the first-line metastatic setting with at least three prescriptions for Palbociclib will be included.
2. Patients were followed for at least 6 months.

Detailed methodology for summary and statistical analyses of data collected in this study for the primary and secondary objectives is documented herein, following the requirements of the Statistical Analysis Plan (SAP) template; therefore a separate SAP document will not be necessary for these analyses.

CCI

A large rectangular area of the page is completely blacked out, indicating that the content has been redacted. The word 'CCI' is printed in red at the top left corner of this redacted area.

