Variables: Variables will be obtained from both structured and unstructured data using Flatiron's technology-enabled data processing. The following variables will be included for the analyses: demographics (eg, age, race, ethnicity, region), baseline clinical characteristics (eg, date of diagnosis of MBC, HR+/HER2- status, ECOG performance status, disease stage at initial diagnosis, site of metastasis, and number of disease sites), treatment patterns (eg, AI therapy partner, starting dose, dose adjustment, duration of treatment, discontinuation, and reasons for dose adjustment and discontinuation), and effectiveness (real-world progression-free survival, overall survival, real-world tumor response, time to next line of anti-cancer treatment, and time to chemotherapy).

Data source

Flatiron Health's longitudinal, demographically and geographically diverse database derived from electronic health record (EHR) data from over 265 cancer clinics (~800 sites of care) including more than 2 million active US cancer patients.

Study Size: Based on an initial feasibility assessment using Flatiron Health Analytic Database between February 2015 – November 2018, there are 1,367 HR+/HER2- MBC patients who received Palbociclib + AI (including 1,221 Palbociclib + Letrozole, 70 Palbociclib + Anastrozole, and 76 Palbociclib + Exemestane) and 627 patients who received Letrozole monotherapy in the database. All patients satisfying inclusion and exclusion criteria will be included in the statistical analyses.

Data Analysis: Descriptive analyses will be performed to describe baseline demographics and clinical characteristics, treatment patterns, and effectiveness outcomes for patients receiving Palbociclib + AI as initial endocrine based therapy for MBC. Kaplan-Meier curves and landmark analyses will be performed to estimate real-world progression-free survival, overall survival, real-world tumor response, and time to chemotherapy from Palbociclib + AI

initiation. Subgroup analyses will be conducted according to age, ECOG performance, metastatic status, menopausal status, and prior therapy.

CCI

Milestones: Data analysis will be conducted once data/related variables are available, and the final study report will be completed on Oct 27, 2021.

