| Real-world tumor responses (rwTR) | Real-world tumor responses are assessed based on treating clinician's assessment of radiological evidence for change in burden of disease over the course of treatment: 
 • Complete response: complete resolution of all visible disease. • Partial response: partial reduction in size of visible disease in some or all areas without any areas of increase in visible disease. • Stable disease: no change in overall size of visible disease; also included cases where some lesions increased in size and some lesions decreased in size. • Progressive disease: an increase in visible disease and/or presence of any new lesions; included cases where the clinician indicated progressive disease. |
| Response rate | Complete response or partial response divided by the number of patients with at least one tumor assessment while on the index treatment |

| | |
|--|--|
| Real-world duration of treatment (rwDOT) | Months from index treatment initiation to end of the treatment |
| Time to next line of anti-cancer therapy | Months from index treatment initiation to next line of anti-cancer therapy or death from any cause, whichever occurred first |
| Time to chemotherapy | Months from index treatment initiation to first use of chemotherapy or death from any cause, whichever occurred first |

Table 2. List of Medications for the Treatment of HR+/HER2- Metastatic Breast Cancer

| Drug Name | Brand Name | Type of therapy | Code |
|-------------------|------------|-----------------|--|
| Anastrozole | Arimidex | Endocrine | S0170 |
| Exemestane | Aromasin | Endocrine | S0156 |
| Fulvestrant | Faslodex | Endocrine | J9395 |
| Letrozole | Femara | Endocrine | N/A |
| Megestrol acetate | Megace | Endocrine | S0179 |
| Raloxifene | Evista | Endocrine | N/A |
| Tamoxifen | Nolvadex | Endocrine | G8376, G8380, G8381, S0187 |
| Toremifene | Fareston | Endocrine | N/A |
| Everolimus | Afinitor | Target therapy | J7527, J8561 |
| Palbociclib | Ibrance | Target therapy | N/A |
| Ribociclib | Kisqali | Target therapy | N/A |
| Abemaciclib | Verzenio | Target therapy | N/A |
| Capecitabine | Xeloda | Chemotherapy | J8520, J8521 |

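### Tumor response (rwTR) is given landmarks to 36 months, and in the abstract Kaplan-Meier estimation, but has no time-to-event definition or censoring rule; censoring patients who stop treatment or die would overstate cumulative response.

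*Protocol*

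**What the plan says.** The protocol treats rwTR in three ways.

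- **As a Kaplan-Meier outcome.** The Data Analysis paragraph of the abstract (section 4) says: "Kaplan-Meier curves and landmark analyses will be performed to estimate real-world progression-free survival, overall survival, real-world tumor response, and time to chemotherapy".
- **As a landmark outcome.** Section 9.7 says: "landmark time points are 3, 6, 12, 18, 24, 30, and 36 months for rwPFS and rwTR". The sentence before it, which lists the Kaplan-Meier outcomes, begins "Kaplan-Meier curves and landmark analyses will be performed to estimate real-world progression-free survival, overall survival, and time on treatment" and goes on to next therapy and chemotherapy. It does not name rwTR.
- **As a category and a proportion.** Table 1 (section 9.3) says: "Real-world tumor responses are assessed based on treating clinician's assessment of radiological evidence for change in burden of disease over the course of treatment", followed by definitions of complete response, partial response, stable disease and progressive disease. Response rate in the same table is "Complete response or partial response divided by the number of patients with at least one tumor assessment while on the index treatment". Section 9.7 agrees: "The maximum real-world tumor response will be computed for each patient with at least one on-Palbociclib + AI treatment tumor assessment", and "If a patient has a maximum tumor response of a CR or PR, then the patient will be considered to be a responder".

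The SAP repeats the four categories and the proportion (section 5.1). It assigns tumor response descriptive and logistic analyses with PSM/IPTW (section 6.1) and lists no Kaplan-Meier figure for it (section 7). Protocol 9.7 states that it serves as the analysis plan for the primary and secondary objectives, with no separate SAP needed for them.

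rwTR belongs to the third primary objective (section 8), while section 9.1 lists it and response rate as secondary endpoints.

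**The concern.** A Kaplan-Meier estimate, or a landmark read from one, needs a time origin, an event date and a censoring rule. Table 1 gives rwPFS and OS a start date, an event and a censoring rule, and defines time to next therapy and time to chemotherapy in months from treatment start to a named event. rwTR has none of these. The seven landmark figures therefore cannot be produced from the variable as defined, and a programmer would have to invent the rule.

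The natural default carries a bias. Only assessments made on index treatment count toward response, so a patient whose index treatment has ended, by stopping or by death, can no longer become a responder under the protocol's own definition. Ordinary Kaplan-Meier censoring treats that patient as still able to respond later. One minus Kaplan-Meier then describes response in a setting where nobody ever leaves treatment. At stake is the late part of a response curve for an outcome named in a primary objective.

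**Working it through.** The documents give no numerical figure for rwTR, so there is nothing to reproduce. The check has two parts.

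**1. Is there a time variable?**

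| Outcome | Time origin and event | Censoring rule |
|---|---|---|
| rwPFS | Index date to progression or death | Next line of therapy or last visit |
| OS | Index date to death | Data cut-off |
| Next therapy, chemotherapy | Index treatment start to that event or death | Given in SAP 5.1 |
| rwTR | None: four categories | None |

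Reading the rwTR landmarks as plain proportions does not close the gap. Index dates run from 3 February 2015 to 31 August 2018, with cut-off 30 November 2018 or later (sections 9.1 and 9.4). At the November 2018 cut-off, anyone indexed after 30 November 2015 has less than 36 months of possible follow-up. A 36-month figure needs a stated denominator or censoring rule, and none is given.

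**2. How much could the handling matter?**

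Inputs:
- Competing-event median: 24.8 months, the PFS median for palbociclib + letrozole quoted in Protocol section 7 and SAP 3.3. It is a stand-in for time to end of treatment or death, which the documents do not give.
- True 36-month cumulative response: 30-60%. This is an assumption; the documents give no value.
- Shape of the response hazard: constant at r, or early-concentrated as a·exp(-t/6) with t in months. Both are assumptions.

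Competing hazard: c = ln 2 / 24.8 = 0.02795 per month.

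Constant hazard:
- One minus Kaplan-Meier, competing events censored: 1 - exp(-r·t)
- Cumulative incidence: r/(r + c) × [1 - exp(-(r + c)·t)]

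Early hazard, with H(t) = 6a·[1 - exp(-t/6)]:
- One minus Kaplan-Meier: 1 - exp(-H(t))
- Cumulative incidence: the integral from 0 to t of a·exp(-u/6)·exp(-H(u) - c·u) du, evaluated numerically

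For each assumed true value, r or a is solved so that the cumulative incidence at 36 months equals it. For example, at a true 60% with constant hazard, r = 0.04953 and r + c = 0.07748. Cumulative incidence is 0.6393 × (1 - exp(-2.789)) = 0.600. One minus Kaplan-Meier is 1 - exp(-1.783) = 0.832. The gap is 23.2 points.

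| True 36-month response | r | 1-KM, constant | Gap (points) | a | 1-KM, early | Gap (points) |
|---|---|---|---|---|---|---|
| 30% | 0.0168 | 45.3% | 15.3 | 0.0705 | 34.4% | 4.4 |
| 40% | 0.0248 | 59.1% | 19.1 | 0.1018 | 45.6% | 5.6 |
| 50% | 0.0352 | 71.8% | 21.8 | 0.1394 | 56.6% | 6.6 |
| 60% | 0.0495 | 83.2% | 23.2 | 0.1867 | 67.3% | 7.3 |

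At 12 months the gap is 2.7-6.1 points (constant) or 3.0-5.3 points (early).

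If patients who stop or die without a response are instead kept in the risk set as non-responders until data cut-off, one minus Kaplan-Meier equals the cumulative incidence and the gap is 0.

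**The case against.** The strongest reply is that the operative text in 9.7 does not put rwTR on a Kaplan-Meier curve. Its Kaplan-Meier list omits rwTR, the following sentence promises confidence intervals on medians for rwPFS, OS and treatment time only, and the SAP plans logistic analyses. On this view the abstract is a loose summary and the landmarks are proportions. The omission is real, and the Kaplan-Meier assignment rests on the abstract. But the abstract is explicit, the landmark phrase in 9.7 remains, and a landmark proportion still lacks a follow-up rule.

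Second, a reader might infer that the response figures will be overstated. The documents do not support that, because neither says that patients who stop or die are censored for rwTR. The bias is conditional on that choice.

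Third, a reader might infer that progression itself rules out response. The documents do not say so: 9.7 takes the maximum over on-treatment assessments with no cut-off at progression. End of index treatment and death do rule it out, because response is counted only on treatment. Whether progression should be added is for the sponsor to state.

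Fourth, a constant response hazard over 36 months gives the large gaps. This stands: with early responses the gap is 4-7 points. Still larger gaps would come from the 14.5-month median, but that is the letrozole-alone figure and does not describe the palbociclib + AI cohort of the primary objectives.

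**Conclusion.** The concern holds as a mismatch between method and variable. rwTR is assigned landmarks to 36 months, and Kaplan-Meier estimation in the abstract, without a time-to-response variable or censoring rule. The abstract, 9.7 and the SAP do not agree on how it is to be analysed.

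The bias is a conditional consequence. If end of treatment and death are treated as ordinary censoring, the 36-month figure is too high by about 15-23 points (constant hazard) or 4-7 points (early responses). If these patients remain at risk as non-responders, the excess is 0. These sizes rest on the 24.8-month stand-in median, the assumed 30-60% true response and the assumed hazard shapes; they are not predictions for this database.

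It would go too far to say that the report will contain two conflicting response figures, or that the planned response rate is biased by this. The maximum-response rate is a proportion with a stated denominator and is untouched. The point is worth correcting because unspecified handling alone can move a reported figure from no error to more than 20 points, and the correction is cheap.

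**What to change.** Choose one of two routes.

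- **Remove it.** Delete rwTR from the Kaplan-Meier list in the abstract and from the landmark list in 9.7. Report the maximum-response proportion with a 95% CI. This is a wording change only and brings the protocol into line with SAP 6.1.
- **Define it.** If response over time is wanted, define time from index date to first on-treatment complete or partial response. Report cumulative incidence at the same landmarks, with end of index treatment and death as competing events, and progression too if it is meant to end response assessment. State the analysis population and the censoring date for patients still on treatment without a response. This adds one output and needs dated response assessments. Late response percentages may be lower than a censoring-based curve would show.

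SAP section 1 says that the primary and most secondary analyses had already been run by Amendment 3.0. Any rwTR landmark figures already produced should therefore be checked for how these patients were handled, and the final report should state the rule used.

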| Lines of therapy | Lines of therapy in the metastatic setting are assigned by Flatiron to evaluate systemic treatment on or after the MBC date |
| Initial prescribed dose | Palbociclib: 125mg, 100mg, 75mg using |
| Dose adjustment | Dose strength other than initial/previous prescription |
| Type of the first dose change | Dose reduction 125mg to 100mg, 125mg to 75mg, 100mg to 75mg Dose increase 75mg to 100mg, 100mg to 125mg, 75 mg to 125 mg |
| Time to the first dose change | Days from index date to first dose change |
| Number of dose adjustment | Number of dose reduction and number of dose increase over the calendar time (quarter since February 2015) and over treatment cycle since index date |
| Reasons for dose adjustment | As categorized by Flatiron |
| Reasons for discontinuation | Disease progress, toxicity, financial, patient request, other |
| Duration of treatment | Days from index prescription order date to end of treatment |
| Combination endocrine partner | Letrozole, Anastrozole, Exemestane |
| Concomitant LHRH Agonists | Goserelin (Zoladex), Histrelin (Vantas), Leuprolide (Eligard, Lupron), Triptorelin (Trelstar) |
| Other concomitant anti-cancer therapies | Chemotherapy (See Table 2 for detail) |
| Effectiveness outcomes | |
| Real-world PFS (rwPFS) | Months from index date to death or disease progression (growth or worsening in the disease concluded by the treating clinician based on radiology, laboratory evidence, pathology, or clinical assessment) whichever came first. If patients did not die or have disease progression, they were censored at the date of initiation of next line of therapy for patients with two or more lines of therapy or their last visit date during the study period for patients with only one line of therapy |
| Overall survival (OS) | Months from index date to the date of death. Patients who did not die period are censored at the time of data cut-off |

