Time to treatment discontinuation	
 
The time from the start of a treatment to the time of treatment discontinuation for any reason in 1LOT
 
Start date: PAL/AI start date in 1LOT
 
End date: 
 
A. PAL/AI end date in 1LOT
 
B. 2LOT start date
 
C. Death date in 1LOT
 
D. Whichever came first
 
 
 
Censoring date: latest available drug administration or latest visit/activity date (lab, office, radiology, etc), end of study, or loss to follow-up, whichever came first.
 
2LOT start date 
 
A. Start date of adding any new anti-neoplastic (chemotherapy, target therapy (eg., Abemaciclib, Ribociclib), or endocrine therapy) if there is evidence of disease progression or after 60 days of index date if there is no evidence of disease progression.
 
B. AI discontinuation or exchange from one AI to another AI is not considered as 2LOT start if there is no evidence of disease progression
 
C. Exchange from one PAL to another CDK4/6i AI is not considered as 2LOT start if there is no evidence of disease progression.
 
D. 1LOT was not advanced if PAL and/or AI were paused or stopped and then restarted within 120. Different days (90, 120, and 180) will be used as sensitivity analyses.
 
 
 

Organ-level metastatic sites	Number of sites; Sites of metastases (bone, lung, liver, brain, distant lymph nodes, other) Visceral vs. non-visceral, bone only
Modified Charlson comorbidity index (CCI)	As defined in the Flatiron database
Effectiveness outcomes	
Overall survival (OS)	
Time in months from index date to death due to any cause or censoring date will be calculated.
 
Based on an improved understanding of the death information in Flatiron and a better understanding of the OS analysis in PALOMA-2 the following changes will be made to the OS outcome definition.
 
Event: Any death recorded by Flatiron in the data extract. Patients who did not die will be censored at the time of data cutoff.

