Real-world PFS (rwPFS)	
Time in months from index date to progression or censoring date will be calculated.
 
Based on improved understanding of the PFS analysis in PALOMA-2 the following changes will be made to the PFS outcome definition.
 
Event: Any death or disease progression (concluded by the treating clinician based on radiology, laboratory evidence, pathology, or clinical assessment). If patients did not die or have disease progression, they were censored at the date of initiation of next line of therapy for patients with two or more lines of therapy or their last visit date during the study period for patients with only one line of therapy.

Real-world tumor responses (rwTR)	
 
● Complete response: complete resolution of all visible disease.
 
● Partial response: partial reduction in size of visible disease in some or all areas without any areas of increase in visible disease.
 
● Stable disease: no change in overall size of visible disease; also included cases where some lesions increased in size and some lesions decreased in size
 
● Progressive disease: an increase in visible disease and/or presence of any new lesions; included cases where the clinician indicated progressive disease.
 

Response rate	
 
● Complete response or partial response divided by the number of patients with at least one tumor assessment while on the index treatment.
 

Time to next line of anti-cancer therapy	
 
● Defined as the time from the initiation of 1LOT (PAL+AI) until either 
 
○ the day before the start of 2LOT for patients with evidence of 2LOT, or
 
○ death if the death occurred within 60 days following the patient's last administration of 1LOT (PalB/AI)
 
○ Whichever occurred first.
 
 
 
● If a patient did not have evidence of 2LOT and did not die within the 60 days following the last 1LOT administration, the patient was censored at the latest available date that occurred on or before the end of study date of either last drug administration plus the number of days in a treatment cycle (last PAL/AI administration + 28 days) last visit date (e.g., office visit, lab, radiology, etc), or data cutoff date.
 

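### Maximum tumor response is not cut off at first progression, so an on-treatment PR read after an rwPFS event can count as a first-line response

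*Protocol*

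**What the plan says.** **Responder rule.** Protocol 9.7: "The maximum real-world tumor response will be computed for each patient with at least one on-Palbociclib + AI treatment tumor assessment". It continues: "If a patient has a maximum tumor response of a CR or PR, then the patient will be considered to be a responder". The rate uses "the number of patients with at least 1 on-treatment tumor assessment as the denominator". SAP 5.1 gives the same rate: "Complete response or partial response divided by the number of patients with at least one tumor assessment while on the index treatment".

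**Window.** Protocol Table 1 (Section 9.3) bases real-world tumor response (rwTR) on the clinician's "assessment of radiological evidence for change in burden of disease over the course of treatment". The rwTR row in SAP 5.1 lists the four response categories but leaves that phrase out.

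**Partial response.** Table 1 defines it as "partial reduction in size of visible disease in some or all areas without any areas of increase in visible disease". Neither document names the scan against which the reduction is judged.

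**Progression.** For rwPFS, Table 1 takes progression as "growth or worsening in the disease concluded by the treating clinician based on radiology, laboratory evidence, pathology, or clinical assessment". That is a wider evidence base than the radiology used for rwTR.

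**End of index treatment.** In the SAP 5.1 row on time to treatment discontinuation, treatment ends at the recorded end date, the start of second line or death. Second line starts under a rule that opens "Start date of adding any new anti-neoplastic (chemotherapy, target therapy" and goes on to endocrine drugs. Progression affects whether some changes advance the line, but it is not itself an end date.

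**The concern.** In Protocol 9.7 the on-treatment condition selects patients and sets the denominator. It does not say which of a patient's assessments may supply the maximum. Even if Table 1's treatment window is read into it, a patient who progresses, stays on the index drug and is scanned again remains inside the window. If that later scan is read as a partial reduction, she has an rwPFS event and is afterwards counted as a first-line responder.

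rwTR is part of a primary objective (Protocol 8), and response rate is a listed secondary endpoint (Protocol 9.1). SAP 6.1 also takes tumor response into logistic regression with propensity-score matching (PSM) and inverse probability weighting (IPTW), and relates it to initial dose and dose adjustment. Treatment beyond progression happens after baseline, so balancing baseline covariates cannot remove a difference in it between groups. Two programmers could also follow the plan and report different rates.

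**Working it through.** The documents state no response rate, expected rate or rwTR sample size, so there is no figure to reproduce. The check has two parts.

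**1. Can a post-progression read enter under the text?**

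- Protocol 9.7 takes the maximum and states no stopping date.
- Table 1 sets the window as the course of treatment.
- The SAP's end-of-treatment dates do not include progression. Protocol Table 1 lists disease progression as one reason for discontinuation among several, which again treats the two as separate events.
- rwPFS progression may be called on laboratory, pathology or clinical grounds, with a radiological read following later.
- The PR definition excludes any area of increase on the scan being read. With no reference scan named, a reduction from the enlarged, progressed state still fits the words.

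So yes: followed as written, such a read counts.

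**2. How large could the effect be?**

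Let q be the share of assessed patients who had no CR or PR before progression and were scanned on index treatment after it. Let s be the chance that such a patient is then read as CR or PR. With the denominator fixed:

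rise in response rate = q × s

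This is never negative, since each extra read can only turn a non-responder into a responder. The documents give neither q nor s, so all values below are assumed.

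| q | s | Rise (percentage points) |
|---|---|---|
| 0% | any | 0 |
| 5% | 10% | 0.5 |
| 10% | 20% | 2.0 |
| 20% | 30% | 6.0 |

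For scale, the feasibility count in Protocol 9.5 is 1,221 + 70 + 76 = 1,367 patients on Palbociclib + AI. If all are assessed, 2.0 points is 0.02 × 1,367 ≈ 27 responders. If 60% are assessed (0.6 × 1,367 ≈ 820, assumed), it is about 16.

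The half-width of a 95% interval at an assumed 50% rate is 1.96 × √(0.25/1,367) ≈ 2.65 points, or 3.42 points with 820 assessed. At 40% or 60% the figures are 2.60 and 3.35.

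**Between groups.** With the same s in both groups, the spurious difference is (q₁ − q₂) × s. At an assumed 20% against 10%, this is 0.10 × 0.10 = 1 point up to 0.10 × 0.30 = 3 points. If q and s are equal in the two groups, it is zero.

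**The case against.** The strongest reply is that a treatment window exists. Table 1 ties rwTR to the course of treatment and the SAP ties the rate to index treatment, so the maximum is not taken over everything in the chart. This stands. A reader might infer from the SAP's shortened rwTR row that responses on later lines count. The documents do not support that as the plan's meaning: the treatment wording remains in Table 1, and Protocol 9.7 says the methods for the primary and secondary objectives are set out in the protocol. The SAP row is loose and should be aligned, nothing more. The window does not answer the point, however, because it closes at the end of treatment and not at progression.

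Second, the SAP line rules are limited evidence. They belong to an outcome that SAP 6.1 says is not meant as an effectiveness measure. Rules B and C withhold line advance for AI discontinuation, an AI exchange or a CDK4/6 inhibitor exchange only where there is no evidence of progression, so such changes may advance the line after it. That narrows the exposed group without emptying it.

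Third, a radiological PR after a non-radiological progression call could be a genuine first-line response, and a cut would discard it. This is fair, and is the reason to keep the uncut rate as a sensitivity analysis.

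Fourth, redacted text or the database vendor's business rules may already contain a cut. That cannot be excluded. But the visible protocol says its methodology is complete for these objectives, so the rule should appear there.

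**Conclusion.** The gap is real: as written, an on-treatment PR read after an rwPFS progression event makes the patient a first-line responder. With the denominator held, the effect is zero or upward.

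Its size is not known. A rise of 0–2 points follows from assumed exposure of 0–10% and PR reads of 5–20%, and 6 points needs 20% and 30%. The lower range lies within the sampling error of the rate at the feasibility sample size.

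Two stronger readings are tempting and not supported. One is that the response rate is inflated: the documents show only that it can be, since they give no rate of treatment beyond progression, of later scans or of PR reads. The other is that the cohort or dose comparison is biased: this follows only if treatment beyond progression, or the chance of a later PR read, differs between the groups. Nothing in the documents shows that it does; the 1–3 points above is an illustration.

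**What to change.** In Protocol 9.7 and SAP 5.1, state that maximum response is the best response among assessments made after the index date and up to and including the earliest of first rwPFS progression, end of index treatment or start of the next line. In addition:

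- Define the denominator as patients with at least one assessment in that same window. If only the numerator were cut, patients whose sole on-treatment scan follows progression would become automatic non-responders. Report how many patients leave the denominator.
- Restore the course-of-treatment phrase in the SAP rwTR row.
- Report the rate without the progression cut as a sensitivity analysis.

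**Cost.** A few lines of text, a date filter and a small re-analysis. Progression and line dates are in data sets listed in SAP 2.1, and assessment dates are already needed to decide who was assessed on treatment. SAP Section 1 says the primary and most secondary analyses were run before Amendment 3.0, so the change should be dated and both rates shown. The reported rate may fall slightly, although dropping non-responders from the denominator works the other way. Any radiological response that follows a non-radiological progression call is lost from the main rate and kept in the sensitivity analysis.
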